#### **12.10.8 Concomitant Medications**

Concomitant medications will be classified using the current version of the World Health Organization Drug Dictionary Enhanced (2012). Concomitant medications are medications taken at least once from 28 days prior to Screening through the End of Study visit.

Medications stopped on the 28 days prior to Screening time point will not be considered a concomitant medication.

Individual data listings will be presented for each subject, with separate listings for prior medications and concomitant medications. In addition, concomitant medications will be summarized by Anatomical Therapeutic Chemical (ATC) classes and PT using frequency counts and percentages. For the summaries of concomitant medications, subjects who take the same medication (in terms of the preferred term) more than once will be counted only once for that medication.

### **12.11 Pharmacokinetics**

#### **12.11.1 Trough Serum Concentrations (All Subjects)**

The following PK parameters will be calculated using validated PK software, WinNonlin, Version 5.3 (or higher; Pharsight Corporation; Cary, NC, U.S.):

- Day 1; Weeks 1, 2, 4, 8, 12, 18, and 24: trough concentration ( $C_{trough}$ )
- Day 1 and Week 12 or Week 24:  $C_{trough}$ ; concentration at 2 hours post-dose ( $C_{2h\ post-dose}$ )

PK data will be used to evaluate the accumulation of NGM282 in the plasma of NASH patients following multiple-dose administration at 3 and 6 mg per day. This will be done by comparing the steady-state trough NGM282 levels in NASH patients to results obtained on Day 1 in the same subject and, more generally, in the dosing cohort. In addition, determination of NGM282 concentrations 2 hours post-dose on Day 1 and EOT will enhance information obtained on accumulation and provide an indication of expected maximum drug concentration ( $C_{max}$ ) in patients. This information will be directly compared to Phase 1 results obtained in healthy volunteers as well as those obtained in patients with T2D, PBC, and primary sclerosing cholangitis. In addition, PK data will be used to explore PK/PD correlations in terms of drug efficacy and toxicity, where data allow. Actual sample times will be used in the data analysis.

### 12.11.2 Single-Dose Pharmacokinetics (Open-Label Single-Blind Subjects)

The Day 1 PK data will be used to evaluate the single-dose PK of NGM282 in PBC patients at 0.3, 1, and 3 mg per day, using the PK population. For each subject, the following PK parameters will be calculated, whenever possible, based on the serum concentrations of NGM282 collected at pre-dose and 1, 2, 4, 8, and 12 hours after dosing on Day 1.

- $C_{max}$  - maximum observed concentration
- $T_{max}$  - time to maximum concentration
- $AUC_{0-t}$  - area under the concentration–time curve from Hour 0 to the last measurable concentration, calculated using the linear trapezoidal rule
- $AUC_{0-\infty}$  - area under the concentration–time curve extrapolated to infinity, calculated using the formula:

$$AUC_{0-\infty} = AUC_{0-t} + \frac{C_t}{\lambda_z}$$

where  $C_t$  is the last measurable concentration and  $\lambda_z$  is the apparent terminal elimination rate constant

- $t_{1/2}$  - apparent terminal elimination half-life, where  $t_{1/2} = (\ln 2)/\lambda_z$
- CL/F - clearance divided by the bioavailable fraction calculated using this formula:  $\text{Dose}/AUC_{0-\infty}$
- $V_z/F$  - volume of distribution based on the terminal portion of the concentration–time curve divided by the bioavailable fraction,  $\text{Dose} / (AUC_{0-\infty} \times \lambda_z)$

The effect of dose level on NGM282 exposure will be assessed by evaluating  $C_{max}$  and  $AUC_{0-t}$ . Any substantial change in  $t_{1/2}$ , CL/F, or  $V_z/F$  with dose will also be noted.

Further details will be specified in the SAP.

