#### **12.4.7 Pharmacokinetic Population**

All randomized/enrolled subjects who receive at least one dose (full or partial) of drug, with a pre-dose (Baseline) blood draw, and at least one qualified (above the limit of quantification) post-dose sample will be included in the PK population. Subjects with protocol violations will be assessed by the medical monitor for inclusion in the PK population. PK summaries and analyses will be conducted using the PK population. The PK population will be based on actual treatment received if it differs from that to which the patient was randomized/enrolled.

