### **12.11.3    Multiple-Dose Pharmacokinetics (Open-label Single-blind Subjects)**

Week 6 PK data will be used to evaluate the effect of repeat dosing and potential accumulation of NGM282 following administration at 0.3, 1, and 3 mg per day, using the PK population. For each subject, the same PK parameters as listed in [Section 12.11.2](#) will be calculated whenever possible, based on the serum concentrations of NGM282 collected at pre-dose and 1, 2, 4, 8, and 12 hours after dosing on Week 6. Where possible,  $AUC_{0-\infty}$ ,  $t_{1/2}$ ,  $CL/F$ , and  $V_z/F$  will be used for the evaluation of time invariance in PK characteristics. Accumulation will be assessed by calculating  $C_{max, Week\ 4}/C_{max, Day\ 1}$  and  $AUC_{0-t, Week\ 4}/AUC_{0-t, Day\ 1}$  for each subject.

In addition to the Week 6 versus Day 1 comparison, accumulation will also be assessed by comparing the trough and 2-hour post-dose NGM282 levels collected over the course of the study.

PK parameters will be estimated, where appropriate, using validated commercial software. Additional software, if required, will be detailed in the SAP. Other parameters may be added as appropriate. PK analysis will use actual times as recorded on the CRF.

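### AUC0-t ends at each subject's last measurable sample, so dose and visit comparisons may cover unequal time spans if low-dose profiles drop below quantification before 12 h

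*Protocol*

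**What the plan says.** Protocol Section 12.11.2 covers 0.3, 1 and 3 mg in the open-label single-blind cohort, using samples "collected at pre-dose and 1, 2, 4, 8, and 12 hours after dosing on Day 1". It defines AUC0-t as the area "from Hour 0 to the last measurable concentration, calculated using the linear trapezoidal rule". It then says: "The effect of dose level on NGM282 exposure will be assessed by evaluating" Cmax and AUC0-t. The same section defines CL/F, "clearance divided by the bioavailable fraction calculated using this formula" Dose/AUC0-infinity, and says that a substantial change with dose in half-life, CL/F or Vz/F will be noted.

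Section 12.11.3 repeats the sampling at Week 6. "Accumulation will be assessed by calculating" each subject's ratio of Cmax and of AUC0-t to Day 1. (The ratios are subscripted Week 4, although the intensive profile is at Week 6; these need reconciling.) AUC0-infinity, half-life, CL/F and Vz/F, where possible, "will be used for the evaluation of time invariance in PK characteristics". In addition, "accumulation will also be assessed by comparing the trough and 2-hour post-dose NGM282 levels collected over the course of the study".

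Section 12.4.7 admits a subject to the PK population with "at least one qualified (above the limit of quantification) post-dose sample". Neither Section 12.11.2 nor 12.11.3 defines an AUC over a fixed interval or says how to compare profiles that end at different times. Both leave further detail to a SAP. The supplied SAP covers only the 24-week histology cohort and excludes PK (SAP Section 2).

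**The concern.** An AUC that stops at the last measurable sample measures both the drug and the assay. Over a tenfold dose range, the lowest dose is the first to fall below the quantification limit. With samples at 4, 8 and 12 h, losing one late sample removes four hours of exposure. Kinetics that are truly dose-proportional could then look more than proportional. A subject whose last measurable time moves between Day 1 and Week 6 gets an accumulation ratio that compares different spans.

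Comparing exposure across doses is a secondary objective (protocol Section 6). Accumulation is also of some interest, because the footnote to Table 1 reports antibody-related accumulation in animals, while Section 5.1.3 reports none in healthy volunteers.

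**Working it through.** The plan gives no figure for this comparison, so there is nothing to reproduce. The check asks what AUC0-t would show if kinetics were exactly linear and unchanged over time.

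**Inputs from the protocol.** Projected AUC is 482 hr·ng/mL at 6 mg (Table 1 footnote). Section 5.4 reports dose-proportional PK in Phase 1. Sampling times are 0, 1, 2, 4, 8 and 12 h. Doses are 0.3 and 3 mg.

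**Assumptions, not in the documents.** One compartment with first-order absorption, ka = 1 per hour, half-life 2 to 4 h, quantification limit (LLOQ) 0.05 to 2 ng/mL.

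**Formula.** Total AUC is A = 482 × dose/6, which gives 24.1 hr·ng/mL at 0.3 mg and 241 at 3 mg. With k = ln 2/half-life,

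C(t) = A·k·ka/(ka − k) × (e^(−kt) − e^(−ka·t)).

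AUC0-t is the linear trapezoid to the last sample at or above the LLOQ.

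**Worked case, half-life 3 h.** At 0.3 mg the concentrations at 1, 2, 4, 8 and 12 h are 3.08, 3.58, 2.74, 1.14 and 0.45 ng/mL.

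- AUC0-4 = 1.54 + 3.33 + 6.32 = 11.20
- AUC0-8 = 11.20 + 2 × (2.74 + 1.14) = 18.96
- AUC0-12 = 18.96 + 2 × (1.14 + 0.45) = 22.14

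At 3 mg every value is ten times higher and 12 h is measurable (4.53 ng/mL), so AUC0-12 = 221.4. The dose-normalised 3 mg/0.3 mg ratio, whose true value is 1.0, is then:

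- 0.3 mg measurable to 12 h: (221.4/3)/(22.14/0.3) = 1.00
- 0.3 mg ends at 8 h: 22.14/18.96 = 1.17
- 0.3 mg ends at 4 h: 22.14/11.20 = 1.98

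**Range of assumptions.** Each cell is the apparent ratio, with the last measurable time at 0.3 mg in brackets.

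| LLOQ (ng/mL) | half-life 2 h | 3 h | 4 h |
|---|---|---|---|
| 0.05 or 0.1 | 1.00 (12 h) | 1.00 (12 h) | 1.00 (12 h) |
| 0.25 | 1.09 (8 h) | 1.00 (12 h) | 1.00 (12 h) |
| 0.5 | 1.09 (8 h) | 1.17 (8 h) | 1.00 (12 h) |
| 1 | 1.67 (4 h) | 1.17 (8 h) | 1.23 (8 h) |
| 2 | 1.53 (4 h)* | 1.98 (4 h) | 2.22 (4 h) |

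*Here the 3 mg profile also ends early, at 8 h.

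A wider grid of 40 scenarios (half-life 1.5 to 8 h, ka 0.7 or 1.5 per hour, LLOQ 0.05 to 1) gave a 0.3 mg/3 mg ratio between 0.55 and 1.00. It was below 1 in 18 scenarios and exactly 1.00 in 22. On AUC0-12 it was 1.00 in all 40.

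**Accumulation.** If the last measurable time is the same at both visits, the AUC0-t ratio is within about 0.01 of the AUC0-12 ratio. If the profile is unchanged but that time moves from 8 to 12 h, the ratio is 1.09, 1.17 or 1.23 for half-lives of 2, 3 or 4 h. A move from 12 to 8 h gives the reciprocal: at 3 h, 1/1.17 = 0.86. With unchanged kinetics there is no reason for one direction to be commoner, and the geometric mean of 1.17 and 0.86 is 1.00.

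**The case against.** The strongest reply is that the problem may never arise. It needs profiles that end before 12 h, and without the LLOQ or half-life nobody can show that from these documents. At an LLOQ of 0.1 ng/mL or below, the table shows no bias. The ratios near 2 come from an assumed LLOQ of 2 ng/mL, which is 56% of the modelled 0.3 mg peak at a 3 h half-life (2/3.58). The PK population rule is only a minimum entry condition and does not show that late samples are expected to be unmeasurable. All of this stands, and it is why the point is conditional.

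The plan also does not rest on AUC0-t alone. CL/F is the reciprocal of dose-normalised AUC0-infinity, and its change with dose is to be noted. AUC0-infinity also feeds Vz/F and the time-invariance check. Cmax, trough and 2-hour levels do not depend on the last measurable time. This stands as partial protection. But Cmax, trough and 2-hour levels are single-point measures, AUC0-infinity is available only where the terminal slope can be estimated, and nothing says which result prevails if they disagree.

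A PK plan for the open-label cohort may already settle the matter; SAP Section 2 says each phase has its own plan, and that one was not supplied.

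A reader might infer that low-dose exposure will be understated, or that the plan builds in a false accumulation signal. The documents support neither. The first depends on assay and half-life figures they do not give. The second would need last measurable times to lengthen systematically while kinetics stay unchanged.

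**Conclusion.** The point holds as a conditional weakness of minor severity. AUC0-t is the named AUC metric for dose effect and for the accumulation ratio, and no common interval is set. If 0.3 mg profiles end at 8 h and 3 mg profiles at 12 h, the apparent dose-normalised ratio is about 1.1 to 1.2 when the truth is 1.0. It rises to roughly 1.7 to 2.2 if 0.3 mg ends at 4 h. If all samples are measurable to 12 h there is no bias. These sizes rest on the one-compartment model, ka of 1 per hour and half-life of 2 to 4 h. For accumulation, the effect is extra noise in subjects whose last measurable time changes.

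Severity is minor for three reasons. The profiles come from about 8 optional subjects per dosing group, with no formal test. The double-blind and 24-week cohorts collect only pre-dose and 2-hour samples, so comparisons with them cannot use AUC0-t. And Section 5.4 bases the choice of 1 mg for the 24-week cohort on histology, non-invasive measures and safety, not on AUC.

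**What to change.** In Section 12.11.2, or in the PK plan for this cohort, compare doses on a dose-normalised AUC over one common observed interval: AUC0-12 where measurable, otherwise the longest interval measurable at all doses, such as AUC0-8. State how samples below quantification are handled. Report AUC0-infinity as support where the terminal slope can be estimated.

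In Section 12.11.3, compute each subject's accumulation ratio over the same interval at both visits, up to the last time measurable at both, and reconcile the Week 4 subscripts with the Week 6 sampling. Keep AUC0-t as a descriptive parameter.

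Extrapolating short profiles to 12 h with the terminal slope is not a substitute. In the model the sampled peak is at 2 h, so a profile ending at 4 h has one sample after the peak and no estimable slope, and this is where the bias is largest.

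The cost is wording only, with no new samples. A shorter shared interval leaves out some late exposure, and subjects without an estimable value must be counted and reported by dose.

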### **12.11.3    Multiple-Dose Pharmacokinetics (Open-label Single-blind Subjects)**

Week 6 PK data will be used to evaluate the effect of repeat dosing and potential accumulation of NGM282 following administration at 0.3, 1, and 3 mg per day, using the PK population. For each subject, the same PK parameters as listed in [Section 12.11.2](#) will be calculated whenever possible, based on the serum concentrations of NGM282 collected at pre-dose and 1, 2, 4, 8, and 12 hours after dosing on Week 6. Where possible,  $AUC_{0-\infty}$ ,  $t_{1/2}$ ,  $CL/F$ , and  $V_z/F$  will be used for the evaluation of time invariance in PK characteristics. Accumulation will be assessed by calculating  $C_{max, Week\ 4}/C_{max, Day\ 1}$  and  $AUC_{0-t, Week\ 4}/AUC_{0-t, Day\ 1}$  for each subject.

In addition to the Week 6 versus Day 1 comparison, accumulation will also be assessed by comparing the trough and 2-hour post-dose NGM282 levels collected over the course of the study.

PK parameters will be estimated, where appropriate, using validated commercial software. Additional software, if required, will be detailed in the SAP. Other parameters may be added as appropriate. PK analysis will use actual times as recorded on the CRF.

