has demonstrated a dose-dependent decrease of Cyp7a1 levels. Consistent with reduction in Cyp7a1 levels, serum C4 levels were also reduced in the 28-day monkey toxicology study ([Study 11-TX-NGM282-1002](#)) and 26-week toxicology study in monkeys ([Study 13-TX-NGM282-1004](#)). Significant reductions in serum C4 levels were also observed after administration of NGM282 in normal volunteers ([Study 12-0101](#)).

NGM282 has also been evaluated in two distinct animal models of NASH. Adeno-associated virus (AAV)-mediated delivery of NGM282 transgenes into FXR-deficient mice demonstrated improvement in the histologic, biochemical, and fibrogenic biomarkers associated with NASH-related hepatic injury (Study 13-PD-NGM282-1007). Similarly, AAV administration of NGM282 in the STAMTM model of NASH in mice showed a significant reduction in steatosis, inflammation, ballooning, and overall body weight versus placebo (data on file).

The safety, tolerability, pharmacokinetics (PK), and pharmacodynamics (PD) of NGM282 have been studied in a blinded, placebo-controlled, single-ascending-dose (SAD)/multiple-ascending-dose (MAD) study in normal subjects ([Study 12-0101](#)). NGM282 or placebo was administered to 119 normal subjects as a daily SC injection in escalating doses of 0.1–30 mg in the SAD module and 0.1–20 mg in the MAD module. Multiple-dose PK were consistent with single-dose PK parameters, with no evidence of drug accumulation. NGM282 was safe and well tolerated with no serious adverse events (SAEs) or clinically relevant laboratory abnormalities. Mild to moderate injection-site reactions (ISRs) were the most common drug-related adverse events (AEs), observed mainly with higher doses and larger injection volumes. NGM282 had a favorable safety profile and highly predictable PK that support once-daily dosing.

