**Table 1. Estimated Safety Exposure Margin of NGM282**

Nonclinical Species	NOAEL (mg/kg) a	Plasma AUC (hr • ng/mL) b	Exposure Margin Relative to Maximum Human Therapeutic Dose c
Monkey	1	6610	~14X
Mouse	3	1062	~2X

AUC = area under the concentration–time curve; hr = hour; NOAEL = no-observed-adverse-effect level.

a Determined from the 6-month chronic toxicity studies.

b Systemic exposure at Day 1 after a single dose was used as the most conservative estimate of exposure given the presence of anti-drug antibody formation with repeat dosing in animals leading to drug accumulation (plasma AUC 7-fold above Day 1 levels).

c Based on a maximal therapeutic dose of 6 mg (0.0864 mg/kg based on a 70-kg patient) where plasma AUC is projected to be 482 hr • ng/mL ([Study 12-0101](#)).

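### Section 12.11.3 applies single-dose clearance and volume formulas to Week 6 data after daily dosing, so Week 6 CL/F and Vz/F are understated by whatever accumulation is present.

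*Protocol*

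**What the plan says.** Protocol Section 12.11.2, on single-dose pharmacokinetics, defines AUC0-inf as the "area under the concentration–time curve extrapolated to infinity, calculated using the formula" AUC0-t + Ct/lambda_z. It gives CL/F as "clearance divided by the bioavailable fraction calculated using this formula" Dose/AUC0-inf, and Vz/F as Dose/(AUC0-inf x lambda_z).

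Section 12.11.3 then turns to repeat dosing: "For each subject, the same PK parameters as listed in" Section 12.11.2 will be calculated from samples "collected at pre-dose and 1, 2, 4, 8, and 12 hours after dosing on Week 6". Where possible, AUC0-inf, half-life, CL/F and Vz/F "will be used for the evaluation of time invariance in PK characteristics". Neither section defines an AUC over a dosing interval or a steady-state clearance.

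Section 5.1.3 describes "highly predictable PK that support once-daily dosing", so the dosing interval is 24 h. It also says that multiple-dose results in healthy volunteers matched single-dose results, without accumulation. Table 1, footnote b, reports a different picture in animals: "anti-drug antibody formation with repeat dosing in animals leading to drug accumulation (plasma AUC 7-fold above Day 1 levels".

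**The concern.** Dose/AUC0-inf equals CL/F only after a single dose. By Week 6 of daily dosing, the area from time 0 to infinity also contains the tails of all earlier doses. The quantity that matches single-dose AUC0-inf under linear, stable pharmacokinetics is the AUC over one 24 h interval. Three of the four parameters named for the time-invariance check (AUC0-inf, CL/F and Vz/F) therefore move with ordinary accumulation even when clearance is constant.

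The stated purpose of Section 12.11.3 is to look at repeat dosing and possible accumulation. A formula that is accurate only without accumulation does not serve that purpose, and it gives the wrong size for any real change in clearance.

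**Working it through.** **Inputs.** Formulas: Sections 12.11.2 and 12.11.3. Interval: 24 h. Sampling: 0, 1, 2, 4, 8 and 12 h. The plan states no Week 6 figure to reproduce.

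The documents do not let a half-life be derived. Table 1 projects an AUC of 482 hr·ng/mL at 6 mg, so CL/F is about 6,000,000 ng / 482 = 12,448 mL/h, or 12.4 L/h. No volume is given. The half-lives below are assumptions.

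**Algebra (linear, one compartment, steady state).**
- AUC0-24 at steady state = single-dose AUC0-inf = Dose/(CL/F).
- AUC0-inf after a steady-state dose = R x single-dose AUC0-inf, with R = 1/(1 - exp(-lambda_z x 24)).
- So Dose/AUC0-inf at Week 6 = true CL/F divided by R, and the same holds for Vz/F.

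Example at 8 h: lambda_z = 0.693/8 = 0.0866; exp(-0.0866 x 24) = 0.125; R = 1/0.875 = 1.143; bias = 0.875 - 1 = -12.5%.

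**Apparent change in CL/F with constant clearance.** The last column simulates 43 daily doses on the protocol's sampling times, with the linear trapezoidal rule, lambda_z from the last three points and an assumed absorption rate of 1.5/h.

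| Half-life | R | Algebra | Simulated |
|---|---|---|---|
| 2 h | 1.0002 | -0.02% | 0.0% |
| 4 h | 1.016 | -1.6% | -1.8% |
| 5 h | 1.037 | -3.6% | -4.0% |
| 6 h | 1.067 | -6.3% | -6.8% |
| 8 h | 1.143 | -12.5% | -13.3% |
| 12 h | 1.333 | -25.0% | -25.8% |
| 24 h | 2.000 | -50.0% | -50.4% |

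By algebra the bias is exp(-lambda_z x 24). It reaches 5% at a half-life of about 5.6 h, 10% at 7.2 h and 20% at 10.3 h.

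**When clearance really falls.** Take a 7-fold fall with volume unchanged, so half-life rises 7-fold. The written formula reports 7 x R, with R at the new half-life:
- 2 h becomes 14 h: R = 1.438, reported fall 10.1-fold.
- 3 h becomes 21 h: R = 1.828, reported fall 12.8-fold.
- 4 h becomes 28 h: R = 2.232, reported fall 15.6-fold.

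**Checking the remedy on the same sampling times.** Each cell is the apparent change in CL/F from Day 1 under constant clearance, for an absorption rate of 1.5/h and then for an absorption half-life of 1 h.

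| Half-life | Formula as written | AUC0-24, linear 12-24 h | AUC0-24, log 12-24 h |
|---|---|---|---|
| 2 h | 0.0 / -0.1% | -2.2 / -3.0% | 0.0 / +0.3% |
| 4 h | -1.8 / -2.1% | -4.1 / -3.1% | 0.0 / +1.7% |
| 8 h | -13.3 / -13.4% | -2.3 / +3.4% | +0.1 / +6.1% |
| 12 h | -25.8 / -24.3% | -1.1 / +10.1% | +0.3 / +11.7% |

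Closing the interval with the linear rule of Section 12.11.2 is worse than the written formula at 2 to 4 h. The log rule avoids this. With the slower absorption it is marginally worse at 2 h (+0.3% against -0.1%) and better from 4 h. Its remaining error at long half-lives with slow absorption comes mainly from Day 1: lambda_z fitted to samples ending at 12 h still carries some absorption, which inflates the extrapolated Day 1 AUC0-inf.

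**The case against.** A reader might infer that stable pharmacokinetics will be reported as a fall in clearance. The documents do not support that. The bias is governed by R, and the only human evidence cited, in Section 5.1.3, is of no accumulation, which puts R near 1 and the bias near zero. The larger figures need half-lives that nothing in the documents indicates. Nor does the animal finding rescue that reading: antibody-linked accumulation would be a real change over time, and the planned check would move in the right direction.

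Section 12.11.3 also sets no test, threshold or decision. It is a descriptive look at an optional subset of about 8 subjects per dosing group (Section 9.9.3 and Synopsis). Half-life, which the fault does not touch, would be reported beside CL/F, as would trough and 2-hour levels. Finally, Section 12.11.2 defers details to a SAP and Section 12.11.3 allows further parameters, while the supplied SAP (Section 2) covers only the 24-week placebo-controlled cohort and sends PK to a separate report.

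These points limit the consequence, and they stand. They do not repair the formula. Permission to add parameters does not replace the ones named for the time-invariance check. Whether an unseen plan corrects them is unknown.

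**Conclusion.** The formula is wrong as written for Week 6. CL/F and Vz/F are understated by the factor 1/R, AUC0-inf is overstated by R, and half-life is unaffected. With constant clearance the size is about 0 to -4% for half-lives up to 5 h, -13% at 8 h and -25% at 12 h; the Phase 1 result favours the low end. A real fall in clearance would be seen but exaggerated, for example 7-fold read as about 10- to 16-fold.

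These figures assume linear one-compartment behaviour, steady state at Week 6 and the half-lives listed. The 7-fold case also assumes unchanged volume and starting half-lives of 2 to 4 h. The fault is certain and its practical size is conditional. Because the repair is a wording change, it should be made.

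**What to change.** In Section 12.11.3, and in the PK analysis plan for the open-label cohort:

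- Define Week 6 CLss/F = Dose/AUC0-24 and Vz/F = Dose/(AUC0-24 x lambda_z).
- Define AUC0-24 as the trapezoidal AUC0-12 plus a 12-24 h segment by the log-trapezoidal rule, using the Week 6 pre-dose value as C24. Use lambda_z for that segment if the pre-dose value is not measurable.
- Judge time invariance by Week 6 AUC0-24 against Day 1 AUC0-inf, and report the extrapolated share of each.

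As a secondary step, use a fixed AUC0-12, where measurable, for the accumulation ratio and the dose comparison. The planned AUC0-t is the "area under the concentration–time curve from Hour 0 to the last measurable concentration", so its end-point can differ between doses. How much that matters depends on a quantification limit that the documents do not give. The same edit should reconcile the accumulation ratios, which are labelled Week 4 although serial sampling is at Week 6.

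The cost is formula wording only, with no new samples. The downside is extrapolation error, because sampling stops at 12 h. In the simulations it stays within 2% for half-lives up to 4 h, but reaches about 12% at a 12 h half-life if absorption is slow.
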